### 1. Study Summary

Project Title	Usability of STAR particles in healthy volunteers: A pilot study
Project Design	Non-randomized, controlled, non-blinded, single-arm pilot (feasibility) study, with an adaptative design at mid trial.
Primary Objective	To identify the most efficacious pressure of administration and the minimum number of rubbing cycles necessary to perforate the stratum corneum.
Secondary Objective(s)	To evaluate sensation and pain during and after STAR particle application.
Exploratory Objective(s)	To assess the dispersion and disposal of the STAR particles. To evaluate the user's feedback on product use.
Research Intervention(s)/Interactions	STAR particles STAR particles are millimeter-scale particles with micron-scale projections made of biocompatible materials that painlessly disrupt the stratum corneum. As STAR particles are rubbed on skin, their microscopic projections create micron-scale pores in the stratum corneum to increase skin permeability to topical compounds independent of physicochemical properties. After the arms of the STAR particle puncture the skin, the elastic forces of the skin push the particles out. Participants will receive the 8 interventions (different application pressures) plus the control (Site and treatment will not be randomly assigned on the arm) by the investigator.
Study Population	Adults (18 to 39 years of age)
Sample Size	20
Study Duration for individual participants	1 visit to screen for medical history, examine skin, obtain informed consent, and application of the STAR particles to the participant's forearm.
Study Specific Abbreviations/ Definitions	GV – Gentian Violet; kPa - kilopascal; microneedle (MN); TEWL – trans epidermal water loss; VAPS – visual analog pain scale
Funding Source (if any)	Aldena Therapeutics (United Kingdom)
Study Site	Emory Children's Center

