#### **4. Study Endpoints**

##### **A. Primary**

- 1) For each primary objective, the **primary endpoint** is the identification of the most efficacious conditions measured by the number of perforations per cm^2 using GV staining and TEWL measurement before and after application of STAR particles [(T0 (before), T20 (after), T30, GV)].

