### **B. STAR particle application**

A 1.5 gram dose of STAR particles (10% concentration in gel) will be applied to the eight application sites (forearm and hand) and 100 mg of the gel without STAR particles will be applied to the control site on one of the forearms. Two rubbing cycles (30 and 60 cycles at a minimum of 1 cycle/second) and three pressures (40, 60, and 80 kPa) will be evaluated. The parameters of each STAR particle application at each site (1-9) are labelled in Figure 1. The investigator will apply the STAR particles with two fingers (index and middle fingers of the dominant hand) and the pressure point of one finger is 1 cm^2. Pressures have been established with the following amount of STAR particles applied to the skin with one finger: 40 kPa (320 grams); 60 kPa (480 grams); and 80 kPa (640 grams). With two fingers, the investigator will apply with a pressure of 40 kPa when scale reads 640 grams; 60 kPa = 960 grams; and 80 kPa = 1280 grams. This will be practiced enough before the study so the investigator will know how much pressure generated on the skin based on previous practice with associating pressure according to scale weight.

[figure not shown]

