### **C. Participants 1-10**

Enrolled healthy adults will receive eight applications (three on each forearm and two to one hand) of STAR particles and one control application on the volar side of one of the forearms for a total of nine applications to the forearms. In addition, two applications of STAR particles will be applied to one of the hands – one application to the palmar surface and one to the dorsum of the hand (Figure 1).

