#### **Application of STAR particles to volar side of each forearm (Figure 1)**

1. Wash participant's arms and hands with disinfecting soap before any application.
2. Allowed skin to dry for at least 10 minutes.
3. Investigator to delimit the 9 areas on participant's forearms and hand with a marker.
4. Measure TEWL  $T_0$  on all 9 sites - measure from areas 1 to 9 and then from 9 to 1, giving 2 measurements for each time point according to Figure 1.
5. Apply STARS (80KPa for 60 cycles) on the dorsum of the closed hand.

6. Apply STARs (80KPa for 60 cycles) to the palmar surface of the same hand.
7. Apply STARs (pressure and # of cycles) to the six areas on the forearms per Figure 1.
8. Extra care will be taken to wash arms and hand with warm water to remove the STAR particles and gel and allowed to dry at least 5 min before the next TEWL ( $T_{20}$ ) is taken.
9. Measure TEWL  $T_{20}$  on all 9 sites - measure from areas 1 to 9 and then from 9 to 1, giving 2 measurements for each time point according to Figure 1.
10. Participant completes Tolerability Questionnaire
11. Participant completes Removal & Disposal Questionnaire and User's Feedback Questionnaire.
12. Pictures (3) will be taken to assess erythema: both forearms and the hand
13. Measure TEWL  $T_{30}$  on all 9 sites - measure from areas 1 to 9 and then from 9 to 1, giving 2 measurements for each time point according to Figure 1.
14. Apply GV staining for 10 minutes on the 2 arms resting with volar arm upward and right hand on a gauze containing GV stain.
15. Wash and wipe off the GV stain thoroughly with ethanol 70%.
16. Take 3 photos of each site to visualize the puncture after GV staining.
17. Using 2 fingers (index and middle), the participant will apply pressure to a kitchen scale in an effort to mimic application of low, medium, and high pressures.
18. The investigator records the weight (from the scale) when the pressure is constant.
19. Participant is discharged.

**Figure 1:** STAR particle application sites for V1 (participants #1-10)

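### In participants 1-10 the pressure/cycle settings appear to sit on the six forearm areas by one non-random map, so a setting cannot be separated from its area without assumptions that the design checks only in part

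*Protocol*

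**What the plan says.** The Study Summary (Section 1) states the allocation rule: "Site and treatment will not be randomly assigned on the arm". Section 6.B defines two cycle counts (30 and 60), and "three pressures (40, 60, and 80 kPa) will be evaluated". It then sends the reader to one figure for the layout: "The parameters of each STAR particle application at each site (1-9) are labelled in Figure 1".

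Section 6.C gives each participant "eight applications (three on each forearm and two to one hand"), plus one gel control on a forearm. Step 7 applies the settings "to the six areas on the forearms per Figure 1", and the figure is captioned "STAR particle application sites for V1 (participants #1-10"). No rotation, counterbalancing or swap of sides is described.

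The primary endpoint (Section 4.A) is the identification of the most efficacious conditions, judged "using GV staining and TEWL measurement before and after application of STAR particles". TEWL is read at every site before application (6.C step 4). Gentian violet (GV) is applied only afterwards (steps 14-16: "Take 3 photos of each site to visualize the puncture after GV staining").

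Section 5 places an interim analysis after 10 participants, which may change area, position, pressure or cycles. Section 6.D gives participants 11-20 STAR particles at 80 kPa and 60 cycles only.

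**The concern.** The primary result is a comparison of settings. If every participant receives a given setting on the same forearm area, the observed difference between two settings is the setting effect plus the difference in how readily those two areas perforate. An area that perforates more easily makes its setting look better, and the reverse. More participants on the same map shrink the random error but leave this component unchanged. Participants 11-20 receive a single setting, so they offer no later chance to separate setting from area.

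**Working it through.** **Inputs.** Settings: 2 cycle counts x 3 pressures = 6 (Section 6.B). Forearm STAR areas: 3 + 3 = 6; with 2 hand sites and 1 control, 9 sites (Section 6.C). Participants on the map: 10. The protocol gives no SD, effect size, power or site gradient, so there is no figure of its own to reproduce. One setting per area is inferred.

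**1. Is setting estimable with free area effects?** Setting df = rank(participant + area + setting) - rank(participant + area).
- One map, n = 10: 15 - 15 = 0 of 5.
- One map, n = 100: 105 - 105 = 0 of 5.
- Settings rotated over areas, n = 10: 20 - 15 = 5 of 5.

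**2. What do assumptions buy on one map?** Six areas give 6 - 1 = 5 between-area df. Additive pressure and cycle effects use (3 - 1) + (2 - 1) = 3. There are 6! = 720 possible layouts.

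| Site effect assumed | Site df | Layouts with all 3 additive df estimable | df left to check fit |
|---|---|---|---|
| Linear gradient over six areas | 1 | 696 | 5 - 3 - 1 = 1 |
| Arm plus linear position | 2 | 468 | 5 - 3 - 2 = 0 |
| Arm plus three free positions | 3 | 0, since 3 + 3 > 5 | none |

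In the last row 564 of the 720 layouts still keep 2 of the 3 df. If the six settings are left free (pressure-by-cycle interaction), they need 5 df, and 5 + 1 > 5 rules out full estimation even beside a linear gradient. These counts run over all possible layouts and do not describe the actual one.

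**3. Do the protocol's own measurements break the tie?** T0 TEWL at each site removes additive level differences. It does not show whether areas respond equally to rubbing. The perforation count has no pre-application value. Reading sites 1 to 9 and then 9 to 1 balances measurement order, not the placement of settings. The single control, the two hand sites (both 80 kPa, 60 cycles) and participants 11-20 carry no information on differences among settings across the six forearm areas.

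**4. How much could it matter? (assumptions only)** Take n = 10, five settings equal and one ahead by a lead L, SE = 1/√10 = 0.316 residual SD, and a linear gradient g that T0 does not remove. The chance of picking the best setting is ∫ φ((x - L - g_b)/SE)/SE · Π_{j≠b} Φ((x - g_j)/SE) dx, averaged over the six areas b that the best setting may occupy.

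| Lead (SD) | No gradient | Range 0.25 SD | 0.5 SD | 1.0 SD |
|---|---|---|---|---|
| 0.5 | 64% | 62% | 57% | 44% |
| 0.75 | 84% | 82% | 77% | about 60% |
| 1.0 | 95% | 94% | 90% | 76% |

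A simulation of the setting F-test (5 and 45 df, 5% level, no true setting effect, 4,000 runs) took area-responsiveness SDs of 0, 0.5 and 1.0 residual SD. On one map it found false differences in 5.4%, 65% and 95% of runs. With the map randomised per participant the rates were 5.2%, 5.4% and 4.8%.

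**5. Precision under rotation.** A cyclic 6 x 6 square plus any four repeated rows (15 choices) keeps all 5 setting df. The variance of a pairwise comparison relative to exact balance is 1.016 on average and 1.021 at most.

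**The case against.** The protocol openly calls this a non-randomised, non-blinded feasibility pilot, so nothing is misstated. The layout sits in a figure that could not be seen, and a non-random layout may still be a thoughtful one. Volar forearm areas may differ little: with a 0.75 SD lead, gradients of 0.25 to 0.5 SD cost only about 2 to 8 percentage points on average, and the large losses need a 1.0 SD gradient that nothing in the protocol supports. The gel control gives some background for the GV count. Section 5 does not say what the interim decision rests on, and Section 6.D already fixes one setting for participants 11-20.

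Much of this stands as a limit on size. It does not remove the aliasing. Disclosure leaves the bias in place, and an analysis plan cannot recover a rotation that the layout lacks.

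A reader might go further and infer that the separating assumptions are wholly untestable, or that no pressure or cycle effect can be estimated. The design does not support that. Beside a linear gradient, 1 lack-of-fit df remains in all 696 estimable layouts, and the 10 participants provide the replication to test it. Even with arm plus free positions most layouts keep 2 of 3 additive df. The real limit is that such a check is joint: a rejection cannot tell a site effect from a pressure-by-cycle interaction, and some gradients would pass unnoticed.

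**Conclusion.** The point holds as a design weakness that should be corrected. On the natural reading of six settings, six areas and one figure for participants 1-10, settings have 0 of 5 df once area effects are free, at any number of participants. Separating them requires assumptions that can be checked only partly and jointly. The primary comparison carries this bias; the interim decision may also carry it, but the protocol does not say so.

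The conclusion rests on one setting per area, which is inferred. The size and direction of the bias are unknown. The correct-pick and false-positive figures show only what assumed gradients would do. They are no ground for saying that this trial will choose the wrong setting.

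**What to change.** 1. Section 1: replace the parenthesis on non-random assignment with: *(In participants 1-10 the six pressure/cycle settings are rotated over the six forearm STAR areas by a pre-printed 6 x 6 Latin square; each row is used once and four randomly chosen rows a second time, allocated to participants in random order.)*
2. Sections 1 and 5: keep the design label and add a separate sentence that, for participants 1-10, the placement of settings on the forearm areas is randomised within participant.
3. Section 6.B: state that Figure 1 gives the area numbers and the hand and control parameters, and that the participant's allocation sheet gives the forearm settings.
4. Section 6.C step 7: refer to the participant's allocation sheet in place of Figure 1, with the six forearm areas treated in area-number order. The hand-first order of steps 5 and 6 is unchanged.
5. Compare settings in a model with participant and site terms.

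Pressures, cycle counts, hand sites and the control site all stay as they are.

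The cost is one printed sheet per participant and these text edits. The map would differ by participant, and pressure is applied by practised feel, so there is some added risk of applying the wrong setting. Recording the applied setting for each area on the sheet reduces it. Ten participants leave the second square incomplete, which raises the variance of a pairwise comparison by about 1.6% on average (at most 2.1%). Setting-versus-control contrasts stay tied to site, because the control site is fixed.

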## **2. Objectives**

### **A. Primary**

1. To identify the most efficacious pressure of administration and minimum number of rubbing cycles necessary for STAR particles to penetrate the stratum corneum.

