**Application of STAR particles to volar side of each forearm**

20. Wash participant's arms and face with disinfecting soap before any application.
21. Allowed skin to dry for at least 10 minutes.
22. Investigator to delimit the 9 areas on participant's forearms and face with a marker.
23. Measure TEWL  $T_0$  on all 4 sites - measure from areas 1 to 4 and then from 4 to 1, giving 2 measurements for each time point.
24. Apply STARs (80KPa for 60 cycles) on the forearm.
25. Apply STARs (80KPa for 60 cycles) to the side of the face.
26. Apply gel without STARs on the other forearm and on the other side of the face.
27. The study team will take photos of the application sites.
28. After approximately 5 minutes, the gel (with or without STAR particles) will be removed with a dry tissue or gauze.
29. The study team will take photos of the areas of application.
30. After the gel is removed in all areas, the investigator will examine the participant to check if there are any remaining STAR particles on the participant and/or the surrounding environment.
31. Participant completes Tolerability Questionnaire
32. Participant completes Removal & Disposal Questionnaire and User's Feedback Questionnaire.
33. Pictures (3) will be taken to assess erythema: both forearms and the face
34. Measure TEWL  $T_{30}$  on all 4 sites - measure from areas 1 to 4 and then from 4 to 1, giving 2 measurements for each time point.
35. Apply GV staining for 10 minutes on the 2 arms resting with volar arm upward and right hand on a gauze containing GV stain.
36. Wash and wipe off the GV stain thoroughly with ethanol 70%.
37. Take 3 photos of each site to visualize the puncture after GV staining.
38. Using 2 fingers (index and middle), the participant will apply pressure to a kitchen scale in an effort to mimic application of low, medium, and high pressures.
39. The investigator records the weight (from the scale) when the pressure is constant.
40. Participant is discharged.

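### Testing only 30 and 60 cycles can bracket, but not locate, the minimum number of rubbing cycles named in the primary objective, and the endpoint for that half favours the largest effect rather than the fewest sufficient cycles

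*Protocol*

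**What the plan says.** The primary objective in protocol section 2.A, repeated in the section 1 summary, has two halves: the most efficacious pressure, and the "minimum number of rubbing cycles necessary for STAR particles to penetrate the stratum corneum".

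Section 6.B fixes the levels: "Two rubbing cycles (30 and 60 cycles at a minimum of 1 cycle/second) and three pressures (40, 60, and 80 kPa) will be evaluated". No other cycle count appears in the protocol.

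Section 4.A sets one primary endpoint and applies it to each primary objective: "identification of the most efficacious conditions measured by the number of perforations" per unit area by gentian violet staining, together with TEWL before and after application.

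For participants 1-10 (section 6.C) the instruction for the forearms is "Apply STARs (pressure and # of cycles) to the six areas on the forearms per Figure 1". The two hand sites are fixed at the higher count, for example "Apply STARs (80KPa for 60 cycles) to the palmar surface of the same hand". For participants 11-20 (section 6.D) the forearm instruction is "Apply STARs (80KPa for 60 cycles) on the forearm". The face site has the same setting, and gel without particles goes on the opposite forearm and the opposite side of the face.

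Section 5 lists the rubbing cycle among the features that may change after the first 10 participants. It names no further level.

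**The concern.** A minimum necessary number is a threshold: the smallest count that achieves penetration. Two tested levels can show on which side of each level the threshold lies, but not where it is. If the 30-cycle sites are perforated, the data are equally compatible with a threshold far below 30.

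The endpoint adds a second mismatch. Looking for the most efficacious condition fits the pressure half, where the aim is the best setting. The cycle half asks for the least that suffices. If more rubbing makes more holes, a search for the strongest condition moves towards 60 cycles even when 30 already perforates the skin.

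What is at stake is the conclusion that the trial may draw on half of its primary objective. A statement that 30 (or 60) cycles is the minimum necessary would go beyond what the design can show.

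**Working it through.** The protocol gives no power, effect size or standard deviation for this objective, so there is no figure of its own to reproduce. Three checks follow.

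**1. What the tested levels can resolve.** Inputs: levels 30 and 60 (section 6.B). Assumption: at a given pressure, if some number of cycles perforates, any larger number does too. Let m be the true minimum.

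| True m | 30 cycles perforates | 60 cycles perforates | Lowest tested level that works | What is known |
|---|---|---|---|---|
| 5, 15 or 30 | yes | yes | 30 | m is at most 30 |
| 31, 45 or 60 | no | yes | 60 | m is 31 to 60 |
| 75 | no | no | none | m is above 60 |

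The largest overstatement when the tested level is reported as the minimum is 30 − 1 = 29 cycles in the first row and 60 − 31 = 29 cycles in the second.

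**2. Where the 30-versus-60 information comes from.** Three pressures × 2 cycle counts = 6 combinations, and there are 6 active forearm sites per person in participants 1-10. Figure 1 is not shown, so one site per combination is assumed.

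- Participants 1-10, forearm: 10 × 3 = 30 sites at 30 cycles and 10 × 3 = 30 sites at 60 cycles.
- Participants 1-10, hand: 10 × 2 = 20 sites, all at 60 cycles.
- Participants 11-20, forearm and face: 10 × 2 = 20 active sites, all at 60 cycles, and 0 at 30 cycles.

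The contrast between cycle counts therefore rests on 10 of the 20 participants. The other 10 contribute 60 cycles against gel.

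**3. Direction of the endpoint.** This illustrates one possible reading of section 4.A, in which the condition with the larger mean is chosen. With 10 within-person pairs at one pressure and a standardised paired difference d in favour of 60 cycles, P(choose 60) = Φ(d × √10). The values of d are assumed.

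| d | d × √10 | P(choose 60) |
|---|---|---|
| 0 | 0 | 0.50 |
| 0.2 | 0.63 | 0.74 |
| 0.5 | 1.58 | 0.94 |
| 0.8 | 2.53 | 0.99 |

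The formula contains nothing about whether 30 cycles is already sufficient. The probabilities are the same whether it is or not.

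**The case against.** The strongest reply is that this is a 20-person feasibility study and that the minimum is naturally read as the lower of the tested levels that works. On that reading the design does give a useful answer, because the three ranges differ in practice. This stands in part: with a criterion for penetration, the study can name the lower sufficient level of the two. Such a criterion may sit in a statistical analysis plan that is not shown, so its absence from the protocol is not counted here. But an analysis plan cannot supply data at untested levels, and the objective speaks of the minimum necessary, not the lowest tested.

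It can also be said that section 4.A never tells the analyst to take the setting with the most perforations, and that the stained sites would show whether 30 cycles perforates whatever the ranking. This is fair. The probabilities in the third check describe an assumed rule and are not a property of the protocol. What remains is that the stated endpoint, applied to every primary objective, is worded for the strongest condition and says nothing about sufficiency.

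Finally, section 5 leaves room to change the rubbing cycle at mid-trial. It does, but it names no level, and section 6.D as written uses 60 cycles throughout.

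Two stronger readings go too far. A reader might infer that participants 11-20 contribute nothing on cycles. In fact they compare 60 cycles with gel, which helps to separate a minimum of at most 60 from one above 60. A reader might also infer that the sponsor expects 30 cycles to work, or that an unsupported minimum would pass into later instructions for use. The protocol says neither.

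**Conclusion.** The point holds as a mismatch between the primary objective, the tested levels and the endpoint. The study can bracket the minimum as at most 30, 31 to 60, or above 60 cycles, and can name the lower sufficient tested level. It cannot identify the minimum itself, and a tested level reported as the minimum could be up to 29 cycles too high. The endpoint in section 4.A fits the pressure half of the objective but does not target the fewest sufficient cycles. The comparison of 30 with 60 comes from participants 1-10 only.

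The bracketing assumes that further rubbing does not undo perforation. The site counts assume that Figure 1 assigns each of the six combinations once. The lean of the endpoint towards 60 assumes that 60 cycles makes more perforations than 30. The documents do not support the wider claim that the study says nothing about the minimum. The change should be made, because it limits what the trial may conclude on a primary objective.

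**What to change.** Keep the pressure half of the objective and its endpoint as they are. Restate the cycle half as two questions: whether the lower tested level is sufficient to perforate the stratum corneum, and whether the higher level adds to it. Give this half its own endpoint, based on sufficiency rather than on the largest effect. State in advance that a positive result at 30 will be reported as no more than 30 cycles, not as the minimum.

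Sections 1, 2.A, 4.A, 5, 6.B and 6.D must be reconciled on this, including whether the second half is meant to inform the cycle question beyond 60 cycles against gel. Whether to study other levels is for the sponsor to decide.

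The cost is the rewording of half an objective and its endpoint, and a slightly less favourable claim. Sample size and procedures need not change.
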